9.1.1 Screening

Before any study-related procedure is performed, parents or legal guardians will provide informed consent for study-eligible patients. Patients will be assessed to determine whether they meet study entry criteria (Section 9.3) and are suitable candidates for implantation of an ICV access device. The diagnosis of CLN2 disease is determined by TPP1 enzyme activity (dried blood spot) in the fibroblasts and leukocytes available at Screening. In addition, blood for TPP1 enzyme activity and CLN2 gene analysis will be collected to be analyzed centrally. Screening procedures are to be completed ≤ 21 days prior to the ICV reservoir implant surgery.

CLN2 rating scales will be performed in full (Appendix 1). Study entry will require a 2-domain ML score of 3-6, as defined in the Ratings Assessment Guideline. The Ratings Assessment Guidelines provide detailed instructions on rating scale assessment, and the Imaging Charter provides instructions on MRI evaluation by a centralized facility. In addition, a complete physical examination will be conducted.

In order to ensure appropriate patients are enrolled in the study (including those with the necessary CLN2 ML scores at Screening), a confirmation of patient study eligibility will be provided to the Investigator by BioMarin. Surgery should not be performed until this approval is obtained. Information that must be provided for Sponsor approval includes (but is not limited to) patient age, results of TPP1 enzyme activity, results of CLN2 genotype testing (if available) and Screening ML score.

9.1.2 Surgery and First Dose

Study subjects will be admitted to the hospital for surgical implantation of an MRI-compatible ICV access device in the lateral ventricle of the right hemisphere; surgery and anesthesia will be under the direction of a neurosurgeon (refer to Study Pharmacy Manual for compatible ICV reservoirs and cannula). An MRI will be performed prior to the surgery to ensure proper planning and placement of the ICV access device. Generally, surgery and postoperative care will be determined by standards of care at the study centers and specific clinical needs of the subject. Subjects will be monitored in a nursing-intensive setting for a minimum of 48 hours post-ICV device placement and after the start of the first drug infusion. Following ICV access device placement, subjects and their caregivers will be given written instructions providing details on signs and symptoms of concern for device complications and instruction on when to return to the site for device evaluation. An additional follow-up telephone call will be conducted within 48 hours after inpatient discharge for all visits.

BIOMARIN¹⁹⁰⁻²⁰³ Amendment 6

The first infusion will occur at least 14 days from surgery to implant the ICV reservoir and no more than 28 days after surgery. In the event that the ICV device is replaced, the next infusion will occur at least 14 days and no more than 28 days after surgery. At the first (and each subsequent) study drug administration, the investigator will evaluate the patency, location, and skin integrity of the reservoir. Access to the device is performed using strict sterile technique. Skin covering the reservoir is inspected for an appropriate needle insertion site. The needle insertion site must be intact, without evidence of breakdown, wound, infection or rash. The needle used is a small gauge non-boring tip. Once the reservoir has been accessed, the needle is immobilized to ensure minimal movement or risk of removal. If the needle dislodges during an infusion, it may not be reinserted, as sterility has been compromised. Guidance for assessing the reservoir devices for leakage and replacement is provided in the Study Pharmacy Manual. At the discretion of the investigator and/or neurosurgeon, the reservoir may be replaced during the clinical study.

9.2 Discussion of Study Design, including Choice of Control Group

This study must be performed in patients with CLN2 disease because neither ICV access device implantation nor potential development of TPP1 autoimmunity, and their unknown long-term health consequences, are acceptable risks for healthy volunteers. However, these risks in a patient population are balanced by the near certainty of severe disability and death within a few years.

The diagnosis of CLN2 disease determined by TPP1 enzyme activity (dried blood spot) in the fibroblasts and leukocytes available at Screening. In addition, blood for TPP1 enzyme activity and CLN2 gene analysis will be collected to be analyzed centrally.

Because CLN2 disease is fatal in childhood, the study population must be children. Because therapeutic benefit is unlikely in advanced CLN2 disease, given the extensive depletion of cortical neurons, lack of extensive CLN2 disease progression is required for study participation, resulting in a study population comparable to that of a TPP1 gene therapy study (Worgall, 2008). Safety evaluation would also be limited in advanced patients, who are essentially in a vegetative state.

A clinical rating scale, the Hamburg Scale, was developed to document the natural history of CLN2 disease (Steinfeld, 2002). A modified form of that scale, the Modified Hamburg Scale, demonstrated statistically significant slowing of neurologic decline in subjects receiving gene therapy intervention when compared with decline among control subjects (Worgall, 2008). A second CLN2 disease rating scale, the Weill Cornell Scale (Dyke, 2012); (Worgall, 2007), has also been used to evaluate CLN2 disease severity with highly comparable results.

BIOMARIN¹⁹⁰⁻²⁰³ Amendment 6

Although all 4 domains of the Hamburg rating scale will be completed (Appendix 1), the motor and language domains are most useful for this study. Language and motor are the earliest domains to lose function, therefore the aggregate CLN2 motor-language scale are appropriate metrics for screening and efficacy. To be eligible for study participation, motor and language domains administered during Screening must document CLN2 disease progression with a 2-domain ML score of 3-6 for these 2 domains, as defined in the Ratings Assessment Guideline. The planned patient enrollment of at least 10 patients is to include at least 5 patients with a combined ML score \geq 5 points (mild disease) and at least 5 patients with a ML score < 5 points (moderate disease) to ensure that an equal number of patients with mild and moderate disease are enrolled. In addition, at least 5 patients < 2 years of age will be enrolled. The effectiveness endpoint will compare motor and language subscale scores of treated study subjects with those of untreated patients acquired from the natural history data of CLN2 disease registries and data from siblings with CLN2 disease, when available.

The remaining 2 domains in the rating scale (Appendix 1) are less likely to be informative for this study. In order to capture the seizure and movement disorder manifestations of CLN2 disease in more detail, adapted domains from the Unified Batten Disease Rating Scale (UBDRS) are incorporated into the protocol. The UBDRS domains record involuntary movements and seizures according to type, frequency and severity (Kwon, 2011).

Because of practical (limited number of available patients) and ethical (neurosurgery in children with fatal neurologic disease) concerns, this study design cannot involve contemporaneous, matched, randomized, blinded, or untreated control subjects (Arkin, 2005); (Crystal, 2004.). Motor and language subscales and total scores for the Hamburg CLN2 disease scale will be compared with historical natural history data from the registry at the University Medical Center in Hamburg, Germany and/or data from siblings with CLN2 disease, as appropriate.

9.3 Selection of Study Population

Pediatric patients (from birth to < 18 years of age) with confirmed CLN2 disease progression may be eligible to participate in this study. Additional criteria for participation in this study are detailed below. Subjects must satisfy the following criteria in order to enroll in the study:

9.3.1 Inclusion Criteria

• Diagnosis of CLN2 disease as determined by TPP1 enzyme activity (dried blood spot) in the fibroblasts and leukocytes available at Screening. *Note: Blood for TPP1 enzyme activity and CLN2 gene analysis must be collected to be analyzed centrally.*

- Quantitative clinical assessment of the Hamburg motor-language aggregate score 3-6 at Screening, as defined in the Ratings Assessment Guideline.
- < 18 years of age at the time of informed consent
- Written informed consent from parent or legal guardian and assent from subject, if appropriate
- Males and females who are of reproductive age should practice true abstinence, defined as no sexual activity, during the study and for 6 months after the study has been completed (or withdrawal from the study). If sexually active and not practicing true abstinence, males and females of reproductive age must use a highly effective method of contraception while participating in the study.
- Ability to comply with protocol required assessments (ICV implantation, drug administration, laboratory sample collection, EEG, ECG, MRI, etc.)

9.3.2 Exclusion Criteria

Individuals who meet any of the following exclusion criteria will not be eligible to participate in the study:

- Another inherited neurologic disease, e.g., other forms of CLN or seizures unrelated to CLN2 disease (patients with febrile seizures may be eligible)
- Another neurological illness that may have caused cognitive decline (e.g., trauma, meningitis, hemorrhage) or interfere with disease rating (autism) before Screening
- Percutaneous feeding tube placement prior to enrollment
- Has received stem cell, gene therapy, or ERT
- Contraindications for neurosurgery (e.g., congenital heart disease, severe respiratory impairment, or clotting abnormalities)
- Contraindications for MRI scans (e.g., cardiac pacemaker, metal fragment or chip in the eye, aneurysm clip in the brain)
- Episode of generalized motor status epilepticus within 4 weeks before the First Dose visit
- Severe infection (e.g., pneumonia, pyelonephritis, or meningitis) within 4 weeks before the First Dose visit (enrollment may be postponed)
- Presence of ventricular abnormality (hydrocephalus, malformation)
- Presence of ventricular shunt
- Has known hypersensitivity to any of the components of BMN 190

BIOMARIN 190-203 Amendment 6

- Has received any investigational medication within 30 days before the first infusion of study drug or is scheduled to receive any investigational drug other than BMN 190 during the course of the study
- Has a medical condition or extenuating circumstance that, in the opinion of the investigator, might compromise the subject's ability to comply with the protocol required testing or procedures or compromise the subject's wellbeing, safety, or clinical interpretability
- Pregnancy any time during the study; a female subject judged by the investigator to be of childbearing potential will be tested for pregnancy

9.3.3 Removal of Subjects from Treatment or Assessment

Subjects (or their legally authorized representatives) may withdraw consent for study participation any time without prejudice; investigators must withdraw from the study any such subject. At the discretion of investigator clinical judgment, a subject may be withdrawn from the study any time. When possible, an Early Termination visit should be scheduled (Section 12.10).

It is a priority of the study to maximize study subject retention and adherence to study-specific procedures. Since study data completeness may affect integrity and accuracy of study results, any subject who suspends or discontinues study treatment should be encouraged to continue study-specific procedures for the remainder of the study. Subjects may suspend or discontinue study medication but should be encouraged to be evaluated per study-specific visit schedule and to undergo all required study procedures and assessments.

The investigator (or designee) must contact the BioMarin medical monitor when a subject discontinues from the study. BioMarin reserves the right to discontinue the study at any time for either clinical or administrative reasons and to discontinue participation of an individual investigator or study site for poor enrollment or noncompliance with the protocol or regulatory requirements.

Reasons for which the investigator or BioMarin may withdraw a subject from the study include, but are not limited to, the following:

- Subject experiences a serious or intolerable AE
- Subject develops a clinically significant laboratory abnormality
- Subject requires medication or medical procedure prohibited by the protocol
- Subject does not adhere to study requirements specified in the protocol
- Subject was erroneously admitted into the study or does not meet entry criteria

• Subject is lost to follow-up

If a subject fails to return for a scheduled visit, a documented effort must be made to determine the reason. If the subject cannot be reached by telephone, a certified letter should be sent to the subject (or the subject's legally authorized representative, if appropriate) requesting that s/he contact the investigator. A copy of this letter and any response should be kept in the study records. If the subject cannot be contacted or fails to respond, the subject will be considered lost to follow-up.

The investigator (or designee) must explain to each subject before enrollment in the study that the subject's protected health information obtained during the study may be shared with the study sponsor, regulatory agencies, and IRB/IEC/REC. It is the responsibility of the investigator (or designee) to obtain written permission to use protected health information per country-specific regulations, such as HIPAA in the US, from each subject or (legally authorized representative, if appropriate). If permission to use protected health information is withdrawn, it is the investigator's responsibility to obtain a written request to ensure that no further data will be collected from the subject, and the subject will be removed from the study.

9.3.3.1 Stopping Criteria

As described in Section 10.2.3.2, all AEs, including toxicity of study drug, will be assessed according to the National Cancer Institute (NCI) Common Terminology Criteria for Adverse AEs (CTCAE) v. 4.0

Hypersensitivity reactions, including anaphylaxis and less severe allergic reactions, are identified risks of ERT. For hypersensitivity or allergic-type reactions, unacceptable drug-related toxicity shall be defined as a NCI CTCAE v. 4.0 Grade 3 or higher AE that is study-drug related in the opinion of the investigator and meets either of the following criteria:

- Shows no improvement with medical intervention, such as infusion interruption, infusion rate reduction, or administration of intravenous antihistamine, oxygen, intravenous fluids, or steroids; or
- Recurs during subsequent infusions at the same or worse severity and intensity, despite any of the following: premedication with appropriate antihistamines, antipyretics, or steroids; and modification of infusion rate.

Instances of unacceptable drug-related toxicity should be discussed by the investigator with the BioMarin medical monitor. A subject who experiences unacceptable drug-related toxicity may be withdrawn from study treatment after consultation with the BioMarin medical monitor.

BOMARIN¹⁹⁰⁻²⁰³ Amendment 6

The normal infusion will be administered over 4 (\pm 1) hours at a rate of 2.5 mL/hr; the dose will be determined by the patient's age. Subjects not receiving the full 300 mg dose (administered in a total volume of 10 mL) will receive the appropriate volume at a rate of 2.5 mL/hr for over a shorter duration of time (See Section 9.4.1). Dosing can be adjusted in the judgement of the investigator, upon consultation with the medical monitor, to manage AEs as outlined in Table 9.4.1.1.

For all events not hypersensitivity or allergic-type reactions, the following will apply:

- If a subject has a Grade 3 or higher AE based on NCI CTCAE v. 4.0 that, in the investigator's opinion, is not related to the subject's underlying disease, consideration will be given to discontinuing the subject from treatment depending on the nature of the event and its persistence. This decision will be made by the investigator in consultation with the BioMarin medical monitor, who may consult the Data Review Board (DRB).
- If two subjects experience the same NCI CTCAE v. 4.0 Grade 3 AE, or if one subject has a Grade 4 AE that, in the investigator's opinion, is not related to the underlying disease, the BioMarin medical monitor will consult the DRB to evaluate the risk/benefit of continuing the study.

Another possible AE is infection from or failure of the indwelling ICV catheter. If an infection is suspected, blood and CSF samples will be drawn for assessment. The subsequent course of therapy, which is guided by site neurosurgical standards of care, may include antibiotic therapy, catheter reposition, or catheter withdrawal. If BMN 190 treatment is suspended, BMN 190 may resume if no more than 4 consecutive missed doses elapse after the last given dose.

If BMN 190 treatment is suspended for any reason, study participation may resume if no more than 4 consecutive doses were missed from the prior given dose.

If two or more subjects experience unacceptable drug-related toxicity, BioMarin may suspend further enrollment in the study pending a review of the data and upon consultation with the DRB. Depending on the nature and severity of the unacceptable drug-related toxicity, dosing of subjects already enrolled in the study may be continued or suspended pending further review. BioMarin will consult the DRB to aid in evaluating the risks of continuing the study and options for modification of the study to minimize subject risk.

Subjects who have a loss of 3 or more points on the combined motor and language components of the Hamburg CLN2 rating scale in any 1 year period may be discontinued at the discretion of the Investigator.

Subjects with a score of 0 on the combined motor and language components of the Hamburg CLN2 rating scale at two consecutive visits will be discontinued from treatment.

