9 INVESTIGATIONAL PLAN

9.1 Overall Study Design and Plan

This will be a Phase 2 open-label, multicenter study in pediatric patients < 18 years of age with CLN2 disease, confirmed by deficiency of TPP1 enzyme activity and mutation of the CLN2 gene. The study is designed to assess disease progression in CLN2 patients treated with BMN 190 compared to natural history data from untreated historical controls (data from a CLN2 disease patient registry and data from siblings with CLN2 disease, when available). The comparison of treatment with untreated controls will be compared from the time of the initiation of study drug. A summary of events is provided by visit in Table 9.1.1

The planned enrollment for this study is at least 10 patients: at least 5 patients with a Hamburg ML score \geq 5 points, at least 5 patients with a ML score < 5 points, and at least 5 patients < 2 years of age. Study eligibility will be determined and enrollment will occur before (\leq 21 days) subjects are admitted to the hospital for surgical implantation of an ICV access device. The Baseline visit to collect clinical scores and clinical laboratory parameters will be completed no more than 2 days before the first infusion.

BMN 190 will be administered every 14 days from the date of the first infusion (\pm 3 days) for at least 144 weeks according to the patient's age:

- birth to < 6 months: 100 mg
- 6 months to < 1 year: 150 mg
- 1 year to < 2 years: 200 mg (first 4 doses), 300 mg (subsequent doses)
- ≥ 2 years: 300 mg

Patients younger than 2 years will start the study at the dose level appropriate for their age and will transition to the dose level consistent with their age as they mature. Upon study completion or early termination, all patients will be given the opportunity to participate in a postmarketing registry that will assess the long-term safety and efficacy of BMN 190 for patients receiving commercial drug.

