Another possible AE is infection from the indwelling ICV catheter. If an infection is suspected, blood and CSF samples will be drawn for assessments. The subsequent course of therapy may include antibiotic therapy and catheter reposition or withdrawal. If BMN 190 treatment is suspended, BMN 190 may resume if no more than 4 consecutive missed doses elapse after the last given dose.

A schedule of planned assessments during the study is provided in Table 9.1.1.

Page 37

Table 9.1.1: Schedule of Events

	Screening ^a		Baseli	ne/First Infusion	Treatment Period Weeks 1 to 144	Study Completion / Early Termination	Device Safety Follow-Up	Safety Follow-Up	
Assessments and Events	≤ 21 days prior to ICV Surgery		≤2 Days prior to first dose	First Infusion Visit (Days 1-6)	Visit every 2 weeks (±3 days)	Proximity to last dose (+3 days)	4 weeks after device removal (±3 days)	6 months after last dose ±1week	
Informed consent/assent ^a	Х								
CLN2 Genotype ^b	X ^b								
Blood for TPP1 Activity and CLN2 gene analysis ^b	Х								
CLN2 disease rating scale ^c	Х) k	X		Q4W	Х	X	Х	
Videotaping (CLN2 disease rating scale) ^c	Х	s days)	Х		Q12W	Х			
Verify criteria for study entry	Х	(14-28							
ECG, 3- or 5-lead ^d		y (1		X ^d					
ECG, 12-lead ^e		over	X	Х	Q24W	Х		Х	
EEG, standard awake ^f		Recovery	X		Q24W	Х			
Cranial MRI ^g	Х	and	X		Q24W	Х			
CSF (cell count, protein, glucose, and culture) ^h		Surgery a		D1, D6	Q2W	Х			
Device patency/infection ⁱ		V St		D1, D6	Q2W				
Administer study drug ^j		ICV		D1	Q2W				
Phone follow-up ^k					Within 48 h	hours after inpatient discharge each visit ^k			
CSF / plasma for PK ¹				D1	Q24W	Х			
CSF / blood for disease-related biomarkers ^m				D1	CSF: Q2W (Wks 1-71), Q8W	Х			

	Screening ^a	Baseline/First Infusion		Treatment Period Weeks 1 to 144	Study Completion / Early Termination	Device Safety Follow-Up	Safety Follow-Up
Assessments and Events	≤ 21 days prior to ICV Surgery	≤2 Days prior to first dose	First Infusion Visit (Days 1-6)	Visit every 2 weeks (±3 days)	Proximity to last dose (+3 days)	4 weeks after device removal (±3 days)	6 months after last dose ±1week
				(Wks 79-145) Blood: Q8W (Wks 1-49), Q12W (Wks 61-145)			
CSF/serum for immunogenicity ⁿ		Х	Q12W	V	Х	X (serum only)	X (serum only)
Vital signs ^o			D1	Q2W	Х	Х	Х
Complete physical examination ^p	X	Х		Q48W	Х		Х
Brief physical examination ^p			D1, D6	Q2W		Х	
Height and weight assessments		Х		Q24W	Х		Х
Neurological examination ^p		Х		Q12W	Х	Х	

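### Protocol 9.3.3.1 ties study participation, not only treatment, to a four-missed-dose limit, contrary to 9.3.3, so ML follow-up after a long interruption could be cut short and the primary slope shortened.

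*Protocol*

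**What the plan says.** Two neighbouring paragraphs of Protocol 9.3.3.1 use the same count of missed doses for different things. The paragraph on catheter infection or failure applies it to the drug, as the Synopsis and Section 9.1 do: "BMN 190 may resume if no more than 4 consecutive missed doses elapse after the last given dose". The next paragraph covers every kind of suspension and applies it to being in the study: "If BMN 190 treatment is suspended for any reason, study participation may resume if no more than 4 consecutive doses were missed".

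Section 9.3.3 sets no limit on missed doses for staying in follow-up: "any subject who suspends or discontinues study treatment should be encouraged to continue study-specific procedures for the remainder of the study". It repeats the request in the next sentence: "Subjects may suspend or discontinue study medication but should be encouraged to be evaluated per study-specific visit schedule". The reason it gives is that incomplete data may harm the integrity of the results.

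On the analysis side, SAP Appendix 2 computes each child's rate of decline from two scores, baseline and the last ML score above zero, with no restriction to on-drug assessments. SAP Appendix 3 limits each matched control's follow-up to that of the treated child and does not consider a match with under 6 months of follow-up.

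**The concern.** The participation sentence presupposes that a child leaves the study when treatment is suspended and may return only within the limit. Section 9.3.3 presupposes that the child never left. At a fifth consecutive missed dose, a site could cite the protocol for either course.

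Interruptions of that length are unlikely to be random. Protocol 7.2 reports two device infections in the earlier treated study that needed antibiotics and device replacement, and SAP 4.6 anticipates pandemic effects. Children who discontinue are not replaced (9.3.4).

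If scoring ends at such an interruption, the child's slope describes mostly time on drug, although the primary analysis is on the ITT population. SAP 4.6 argues that missing ML scores matter little because progression is close to linear, but that does not cover a slope that may change when drug stops. The time-to-event analyses are also exposed: they judge reversal at the last recorded observation (SAP 13.1.3) and assume data are missing at random (SAP 4.6).

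**Working it through.** The plan gives no figure for this point and no power calculation, so there is nothing of its own to reproduce. The check is a comparison of texts followed by an illustration.

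**Length of the interruption.** Section 9.1 sets the interval: "BMN 190 will be administered every 14 days from the date of the first infusion". With four missed doses, the gap between given doses is 5 × 14 = 70 days. A fifth missed dose is therefore due 70 days, or 10 weeks, after the last one given.

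**Assessments at stake.** ML is scored every 4 weeks, at Weeks 5, 9, ..., 145: (145 − 5)/4 + 1 = 36 scorings. Take a last dose at Week 47 and missed doses at Weeks 49 to 57. Ending follow-up then loses Weeks 61 to 145, (145 − 61)/4 + 1 = 22 scorings. These counts describe lost data, not the effect on the slope, which uses only two scores.

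**Effect on the slope.** Inputs and assumptions:
- On-drug decline 0.27 points per 48 weeks and untreated decline 2.12, both from the earlier study (Protocol 7.2). Their difference, 2.12 − 0.27 = 1.85, agrees with the protocol.
- Off-drug decline is not given. I assume 0.27, 1.0 or 2.12.
- 14 treated children (SAP Appendix 3).
- Decline is treated as continuous; a score that rounds to zero counts as zero.

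Formula (SAP Appendix 2): rate = (baseline − last score above zero) / weeks × 48.

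Baseline ML 6, drug stopped for good at Week 48, off-drug rate 2.12:
- Last score at Week 48: 0.27 / 48 × 48 = 0.27.
- Last score at the 6-month follow-up, about Week 74: (0.27 + 26/48 × 2.12) / 74 × 48 = 0.92.
- Followed to Week 144: (0.27 + 96/48 × 2.12) / 144 × 48 = 1.50.

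| Off-drug rate | Ends Week 48 | Ends about Week 74 | Ends Week 144 | Shift in mean of 14, Week 48 v 144 |
|---|---|---|---|---|
| 0.27 | 0.27 | 0.27 | 0.27 | 0 |
| 1.0 | 0.27 | 0.53 | 0.76 | 0.035 |
| 2.12 | 0.27 | 0.92 | 1.50 | 0.088 |

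The shift is the difference in slope divided by 14; for the last row, (1.50 − 0.27)/14 = 0.088. Across stopping at Week 24, 48 or 96 and baseline ML 3 or 6, it runs from 0 to 0.11. The top value is baseline 6, stop at Week 24, off-drug rate 2.12: (1.81 − 0.27)/14 = 0.11.

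**Scores taken after the last dose reduce this.** In the Week 48 case with rate 2.12:
- An Early Termination score 10 weeks after the last dose gives (0.27 + 10/48 × 2.12) / 58 × 48 = 0.59, and a shift of (1.50 − 0.59)/14 = 0.065.
- A 6-month score gives (1.50 − 0.92)/14 = 0.04.

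**Against the earlier difference of 1.85.** One child of the Week 48 type, with off-drug rate 2.12, corresponds to 1.85 − 0.09 = 1.76. Three correspond to 1.85 − 0.26 = 1.59.

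**The case against.** The strongest reply is that the consequence is limited and partly answered elsewhere. Most of that stands.

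- **Automatic withdrawal.** A reader might infer that a child is removed at the fifth missed dose. No section says so. The participation sentence says a child may resume, 9.3.3 says should be encouraged, and the non-exhaustive list of withdrawal reasons in 9.3.3 does not include missed doses. Loss of follow-up is a risk, not a certainty.
- **A missing slope, or 22 of 36 scorings as the effect.** Intermediate scores do not enter the two-point slope. SAP 4.6 says all subjects were followed for more than 6 months, so the matching minimum is not threatened.
- **Off-drug decline never observed.** ML is scored at Early Termination, Device Safety Follow-Up and the 6-month Safety Follow-Up (12.10 to 12.12), and SAP Appendix 1 has a Week 169 window. The last two visits can be waived for children who continue to receive or have access to BMN 190, so this protection is partial.
- **An unworkable Early Termination visit.** A column heading in Table 9.1.1 ties that visit to the last dose, and a reader might conclude the schedule cannot be met. The text of 9.1, the note under the table and 12.10 time it from discontinuation, so at most the heading is loose.
- **Shortened controls as a second harm.** Cutting controls to the same duration keeps follow-up symmetric and is not itself a bias.
- **Frequency.** Device replacement alone should not produce such a gap: 9.1 puts the next infusion 14 to 28 days after surgery, against 70 days for a fifth missed dose. SAP 4.6 also promises additional pandemic analyses as appropriate.

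None of this removes the conflict between 9.3.3 and 9.3.3.1. Section 9.3.3 asks for the off-drug scores, and the participation sentence gives a site grounds not to collect them.

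**Conclusion.** The contradiction is established from the text: one sentence of 9.3.3.1 makes participation depend on the missed-dose count, the parallel passages limit only the drug, and 9.3.3 asks for continued visits without any such limit. If the sentence were followed, the primary slope for an affected child would be shortened and weighted towards on-drug time.

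The size is modest: about 0 to 0.11 points per 48 weeks on the treated mean for each affected child among 14. It is zero if decline off drug equals decline on drug, and favours treatment if decline is faster off drug. The upper figure assumes off-drug decline at the untreated rate and no score after the last dose; Early Termination or follow-up scores bring it down. The range rests on rates from the earlier study and an assumed off-drug rate. The documents do not report how many children, if any, missed more than four consecutive doses, so no total effect can be stated.

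**What to change.** Reconcile 9.3.3 and 9.3.3.1, together with the Synopsis and 9.1, so that any missed-dose limit is stated separately from study participation. State in 9.3.3.1 that scheduled CLN2 scoring and safety collection continue, as 9.3.3 already asks, while treatment is suspended and after it is stopped.

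Which re-dosing rule applies, and to which kinds of suspension, is for the sponsor to decide. Simply putting the drug's name in place of participation in the all-causes sentence would settle that question, so it is not proposed here.

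The cost is protocol wording, with ethics review under 14.6 if the change is not merely administrative, plus attendance at visits that are already scheduled and already requested by 9.3.3. No change to the SAP slope or matching is needed.
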